7.4.1 Analysis of Co-Primary Endpoint of OS (Second Interim and Final only)

The co-primary efficacy endpoint of OS will be analyzed on ITT for primary analysis. In order to compare the OS between ASP2215 and the salvage chemotherapy, the null hypothesis will be constructed:

• H_{01} : OS in ASP2215 is worse or equal to the OS in salvage chemotherapy

The accompanying alternative hypothesis is:

• H₁₁: OS in ASP2215 is better than the OS in salvage chemotherapy

The co-primary endpoint of the OS will be tested only at second interim and final analyses. The one-sided p-value for the above hypothesis test will be performed using the stratified log-rank test (primary test) with strata (per IRT) to control for response to first-line AML therapy and preselected salvage chemotherapy.

The SAS code to implement stratified log-rank will be similar to that shown below:

```
PROC LIFETEST;
    TIME time * status (1);
    STRATA stratification variables/group=treatment;
RUN;
```

The hazard ratio of the treatment effect along with 95% confidence interval will be calculated by the stratified Cox proportional hazard model. The same stratification factors will be applied to both the stratified log-rank test and the stratified Cox proportional hazard model. The same Cox proportional hazard model will be included as a sensitivity analysis for testing H_{01} .

The SAS code to calculate the hazard ratio of the treatment effect along with 95% confidence interval will be similar to that shown below:

```
PROC PHREG;

MODEL time * status (1) = treatment/RL;

STRATA stratification variables;
RUN;
```

Stratification variables will include response to first-line AML therapy and preselected salvage chemotherapy.

Kaplan-Meier survival plots will be used to describe the OS in each treatment group. Median OS and 95% confidence interval, survival rates at 6, 12, 24 and 36 months and 95% confidence interval will be estimated from the Kaplan-Meier curve using the SAS code similar to that shown below:

```
PROC LIFETEST DATA=XX TIMELIST=(XX XX XX);
    TIME time * status (1);
    STRATA treatment;
RUN;
```

Where TIMELIST option contains timepoint of interest to estimate survival rate.

Sensitivity analyses for OS include:

- The same analysis as primary analysis but on FAS
- The same analysis as primary analysis but on PPS

- Stratified Cox proportional hazard model with strata to control for response to first-line AML therapy and preselected salvage chemotherapy on ITT
- The same analysis as primary analysis but with OS censoring at HSCT as defined in Section 6.1.1
- The same analysis as primary analysis but with OS censoring at first new antileukemia therapy as defined in Section 6.1.1
- Stratified Cox proportional hazard model with strata to control for response to firstline AML therapy and preselected salvage chemotherapy and initiation of new antileukemia therapy as a time-dependent binary covariate on ITT
- Additional sensitivity analysis will be performed using a new test for equality of two survival functions based on weighted differences of Kaplan–Meier curves with estimation of difference of Restricted Mean Survival Time (RMST) and its 95% CI (Uno et.al, 2015) by a pre-specified cutoff time at 18 months. The 18-month time-point was determined to ensure that reasonable number of patients were still at risk at the cutoff.
- The same analysis as primary analysis will be performed by dose adjustment for subjects whose dose was increased (200 mg dose), decreased (80 mg dose) or remained at 120 mg in ASP2215 arm.

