- q. Includes Brief Fatigue Inventory, Functional Assessment of Chronic Illness Therapy–Dyspnea-Short Forms, Functional Assessment of Cancer Therapy-Leukemia and dizziness and mouth sores items. The BFI will be administered at cycle 1 day 1 predose, cycle 1 day 8 (± 1 day), day 15(± 1 day), cycle 2 day 1 (± 2 days), day 15(± 1 day) and all subsequent cycles day 1 (± 2 days). Functional Assessment of Chronic Illness Therapy–Dyspnea-Short Forms, Functional Assessment of Cancer Therapy-Leukemia and dizziness and mouth sores items will be administered at cycle 1 day 1 predose, cycle 2 day 1 (± 2 days) and all subsequent cycles day 1 (± 2 days).
- r. If possible, patient reported outcome measures should be performed prior to any other assessments on that visit day.
- s. A cycle 1 day 8 ECG will be taken and the central read results will be provided to the site 24 hours after receipt of the tracing. A confirmatory ECG should be performed on cycle 1 day 9 if the mean QTcF from cycle 1 day 1 to cycle 1 day 8 has increased > 30 ms with no other known etiology, based on the central read ECG. On cycle 1 day 8, it is recommended that the ECG is taken as early as possible in the morning and transmitted immediately. In addition, it is recommended that the cycle 1 day 9 visit is scheduled later in the day in order to allow for receipt and assessment of the cycle 1 day 8 central read ECG. This also allows for a subject to be contacted if the cycle 1 day 9 ECG is no longer required. If the cycle 1 day 9 ECG is still required, the result of the central read ECG will be received on cycle 1 day 10, in which the investigator should assess if the ASP2215 dose modification should occur as per the dose interruption or reduction guideline in Section 5.1.2 of the protocol.
- t. Thyroid function tests will be repeated after every 2 cycles of therapy (C3D1, C5D1, C7D1, etc.).

Table 2 Schedule of Assessments for Chemotherapy Arm

	Screening		Cv	cle 1		Cvo	ele 2	Subsequent Cycles
Activity	(Day -14		Day 4	Day 8	Day 15	Day 1	Day 15	Day 1
	to -1)	Day 1	± 1	± 1	± 1	± 2	± 1	± 2
Signed ICF	X							
Medical and Disease History	X							
Randomization		X^p						
Physical Examination ^b	X	Xa	X	X	X	X	X	X
Vital Signs	X	Xa	X	X	X	X	X	X
ECOG Performance	X	Xa			X	X	X	X
Prior and Concomitant Medications	X ^c	X	X	X	X	X	X	X
Pregnancy Test for Woman of Childbearing Potential	X ^d	X				X		X
Chest X-ray (or CT of chest) ^o	X							
12-lead ECG ^e	Xg	X			X	X		X

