6.1.1 Co-Primary Efficacy Endpoint of OS (Second Interim and Final only)

Overall survival (OS) is one of the co-primary efficacy endpoints. OS will be evaluated at the second interim and final analysis. No formal evaluation on OS will be conducted at the first interim. OS is defined as the time from the date of randomization until the date of death from any cause (death date - randomization date + 1). For a subject who is not known to have died by the end of study follow-up, OS is censored at the date of last contact (date of last contact - randomization date + 1).

The date of last contact is the latest date that the subject is known to be alive by the cutoff date. The last contact date will be derived for subjects alive at the analysis cutoff date. Subjects with last contact date beyond the analysis cutoff date will be censored at the analysis cutoff date.

As a sensitivity analysis, OS will be defined similarly as the above primary analysis, however, subjects who undergo an HSCT will be censored at the time of HSCT (HSCT date – randomization date +1).

In addition, as another sensitivity analysis, OS will be defined similarly as the above primary analysis, however, subjects who initiate any new anti-leukemia therapy will be censored at the time of first new anti-leukemia therapy (first new anti-leukemia therapy date – randomization date +1).

During second interim analysis and final analysis, only death events occurring on or prior to the cutoff date are counted as OS events. Subjects with death date after the cutoff date will be censored at the cutoff date.

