7 STATISTICAL METHODOLOGY

7.1 General Considerations

For continuous variables, descriptive statistics will include the number of subjects (n), mean, standard deviation, median, minimum and maximum. When needed, the use of other percentiles (e.g., 10%, 25%, 75% and 90%) will be specified in the relevant section. In addition, for plasma concentrations, the coefficient of variation and the geometric mean will also be calculated. Frequencies and percentages will be displayed for categorical data. Percentages by categories will be based on the number of subjects with no missing data, i.e., will add up to 100%.

SAP Final Version 4.0

Summaries based on ITT (e.g., disposition) will be presented by randomized treatment group, unless specifically stated otherwise. Safety analysis and other summaries based on SAF will be presented by actual treatment received. Pharmacokinetic summaries based on PKAS will be presented by actual treatment received. For subjects with dose increase/decrease, actual treatment refers to the initial dose received before dose change.

All statistical comparisons will be made using two-sided tests at the α =0.05 significance level unless specifically stated otherwise. All null hypotheses will be of no treatment difference, all alternative hypotheses will be two-sided, unless specifically stated otherwise.

All data processing, summarization, and analyses will be performed using SAS® Version 9.3 or higher on Statistical Computing Environment. Specifications for table, figure, and data listing formats can be found in the TLF specifications for this study.

Baseline is defined as the last available measurement prior to the first dose of study drug. Unless otherwise specified, all summaries will be presented by treatment groups.

For the definition of subgroups of interest please refer to Section 7.8.

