CR rate along with the two-sided 95% exact confidence interval based on binomial distribution will be calculated for each treatment group using SAS code similar to that shown below:

```
PROC FREQ;
```

```
TABLES outcome/BIONOMIAL (EXACT);
BY treatment;
RUN:
```

The sensitivity analysis for CR rate will be performed as following:

- The same analysis as primary analysis but on FAS
- The same analysis as primary analysis but on PPS
- The same analysis as primary analysis but only including subjects who received at least one dose of study treatment
- The same analysis as primary analysis but only including subjects who had at least one post baseline bone marrow assessment
- Apply the same analysis method used for primary analysis to evaluate CR rate prior to HSCT (as defined in Section 6.1.3.1)
- Un-stratified Fisher's exact test on ITT
- The same analysis as primary analysis for CR rate will be performed by dose adjustment in ASP2215 arm.

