7.4.3.2 Other Secondary Efficacy Analysis

At the first interim analysis, Duration of CR/CRh (DCRCRh) will be summarized descriptively by median, corresponding 95% confidence interval and range as estimated from the Kaplan-Meier curve. DCRCRh will be analyzed for subjects who achieved either CR or CRh in the same analysis set of CR/CRh rate. Duration of CRh (DCRh) will also be summarized similarly as duration of CR/CRh but for subjects who achieved CRh only.

Transfusion status (independent vs. dependent) at baseline period and post-baseline period will be summarized in a two-by-two contingency table.

Transfusion conversion rate and transfusion maintenance rate will be calculated based on the transfusion status. 95% confidence interval will be presented for both transfusion conversion and maintenance rates.

LFS and duration of remission (including DCRc, DCR, and DR) will be analyzed for subjects who achieved remission using the stratified log-rank test with strata to control for response to first-line AML therapy and preselected salvage chemotherapy. The hazard ratio of the treatment effect along with 95% confidence interval will be calculated. The survival curve and the median will be estimated using the Kaplan-Meier method and will be reported along with the corresponding 95% confidence interval.

CRc rate and transplantation rate will be analyzed in the same manner as CR rate using CMH test to control for response to first-line AML therapy and preselected salvage chemotherapy. The number and percentage of subject with CRc and transplantations will be summarized for each treatment group along with exact 95% confidence interval based on binomial distribution. The treatment difference along with 95% confidence interval will also be calculated. The CRc rate will be summarized by dose adjustment in ASP2215 Arm.

BFI global fatigue score will be summarized using mean, standard deviation, minimum, maximum and median by treatment group at each visit. Additionally, a within-subject change will be calculated as the post-baseline measurement minus the baseline measurement and summarized in the same way. Change from baseline BFI score will be analyzed using Analysis of Covariance (ANCOVA) including treatment as a fixed factor, baseline BFI score, response to first-line AML therapy and preselected salvage chemotherapy as covariates.

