7.4.5 Analysis of Other Variables

Best Response will be summarized by treatment group. The number and percentage of subjects in each category will be presented. The best response rate by prior FLT3 inhibitor use will also be summarized.

At the first interim analysis, Time to first and best CR/CRh (TTCRCRh) will be summarized using descriptive statistics (mean, standard deviation, minimum, maximum and median) for subjects who achieved either CR or CRh in the same analysis set of CR/CRh rate.

TTCRc, TTCR, TTR will be summarized by treatment group using descriptive statistics (mean, standard deviation, minimum, maximum and median) for subjects who achieved remission in the ITT.

7.4.6 Analysis of CR/CRh rate, Duration of CR/CRh and Time to first and best CR/CRh at Final Analysis

The CR/CRh rate, Duration of CR/CRh and Time to first and best CR/CRh will be summarized descriptively on both arms at the final analysis.

The CR/CRh rate will be evaluated in the same manner as CR rate using CMH test to control for response to first-line AML therapy and preselected salvage chemotherapy on ITT. The number and percentage of subjects with CR/CRh will be summarized for each treatment group along with exact 95% confidence interval based on binomial distribution. The treatment difference along with 95% confidence interval will be calculated.

The sensitivity analysis for CR/CRh rate will be performed to assess the robustness of the CR/CRh rate as follows:

- The same analysis as primary analysis but on FAS
- The same analysis as primary analysis but on PPS

Sponsor: Astellas Pharma Global Development, Inc.

ISN/Protocol 2215-CL-0301

- The same analysis as primary analysis but only including ITT subjects who took at least one dose of study drug
- The same analysis as primary analysis but only including ITT subjects who had at least one post baseline bone marrow assessment
- Apply the same analysis method used for primary analysis to evaluate CR/CRh rate prior to HSCT (as defined in Section 6.1.2)
- The same analysis as primary analysis for CR/CRh rate will be performed by dose adjustment in ASP2215 arm.

Duration of CR/CRh (DCRCRh) and Time to first and best CR/CRh (TTCRCRh) will be summarized in the same manner as Duration of CR (as specified in Section 7.4.3.2) and Time to CR (as specified in Section 7.4.5), respectively, for subjects who achieved either CR or CRh on ITT. Median follow-up of DCRCRh estimated from reverse Kaplan-Meier curve will be provided.

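### The OS sensitivity analysis split by later ASP2215 dose change lets survival decide group membership, so it cannot test whether the OS result is robust

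*SAP*

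**What the plan says.** SAP Section 6.1.1 fixes the time origin: "OS is defined as the time from the date of randomization until the date of death from any cause". In Section 7.4.1 the primary analysis is a stratified log-rank test on the ITT set, with a hazard ratio from a stratified Cox model. The last item in that section's list of sensitivity analyses reads: "The same analysis as primary analysis will be performed by dose adjustment for subjects whose dose was increased" (200 mg), decreased (80 mg) or left at 120 mg in the ASP2215 arm. No landmark, restart of the clock or time-dependent term is given for it. The text does not say whether each dose group is compared with chemotherapy or with the other dose groups. It also does not place a subject who had both an increase and a decrease, or one who was never dosed.

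The same list handles another post-randomization event differently, entering "initiation of new antileukemia therapy as a time-dependent binary covariate on ITT".

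The split recurs for response endpoints. Section 7.4.3.1 states: "The same analysis as primary analysis for CR rate will be performed by dose adjustment in ASP2215 arm". Section 7.4.6 states: "The same analysis as primary analysis for CR/CRh rate will be performed by dose adjustment in ASP2215 arm". For CRc, Section 7.4.3.2 plans less: "The CRc rate will be summarized by dose adjustment in ASP2215 Arm".

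**The concern.** The groups are defined by something that happens after the clock starts. Time from randomization to the dose change is guaranteed survival for anyone in a changed-dose group, and a subject who dies before a change could be made is counted as unchanged. This is immortal-time bias, and it arises against either comparator. Against chemotherapy there is a further problem: the control arm has no matching split, so the comparison is no longer randomized.

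A sensitivity analysis of a co-primary endpoint should show whether the main result survives a change in assumptions. This one answers no such question, and readers could take its output as evidence about dose changes.

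For CR and CR/CRh the endpoint is binary, so there is no time-origin problem. The split still conditions on survival and on the course of response, in an uncertain direction. That part is secondary.

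**Working it through.** **Inputs from the SAP (Section 4).** Median OS 5 months on chemotherapy and 7.7 months on ASP2215, hazard ratio 0.65; 246 v 123 subjects; 258 deaths; one-sided alpha 0.0245; about 90% power.

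**The plan's own figure.** Schoenfeld: D = (z_0.0245 + z_0.10)² / [(2/9)(ln 0.65)²] = (1.969 + 1.282)² / (0.2222 × 0.1856), which gives 257 deaths. With 258 deaths the power is 90.2%. The stated figure reproduces. It confirms the inputs but does not bear on the dose split, for which the SAP gives no figure.

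**Mechanism.** With exponential survival and a 5-month median, mean survival is 5/ln 2 = 7.21 months. A subject whose dose changes at month 1.5 has already lived 1.5 months, so expected total survival is 1.5 + 7.21 = 8.71 months. Ignoring censoring, the ratio of crude death rates is 7.21/8.71 = 0.83, with no drug or dose effect at all.

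**Simulation with random dose change.** Assumptions not in the SAP: change uniform over the window, if alive, with probability 0.3 or 0.5; censoring at 24 months; single-covariate Cox model; 600,000 subjects allocated 2:1. The last column uses 3,000 null trials of 246 v 123 per setting and an unstratified log-rank test; the changed-dose group is only part of the 246. Each cell gives the result for 0.3 / 0.5.

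| Window (months) | Null HR, changed v chemotherapy | Null HR, changed v unchanged | True HR 0.65: changed v chemotherapy | Null trials with changed v chemotherapy below 0.0245 |
|---|---|---|---|---|
| 0.33-1 | 0.915 / 0.907 | 0.883 / 0.839 | 0.605 / 0.600 | 7.7% / 10.3% |
| 0.5-1 | 0.907 / 0.904 | 0.865 / 0.821 | 0.595 / 0.596 | 8.9% / 12.5% |
| 1-2 | 0.818 / 0.814 | 0.765 / 0.701 | 0.552 / 0.545 | 21.9% / 31.1% |
| 1-4 | 0.732 / 0.730 | 0.671 / 0.598 | 0.500 / 0.495 | 43.9% / 60.0% |
| 1-6 | 0.667 / 0.657 | 0.602 / 0.530 | 0.459 / 0.456 | 63.2% / 80.2% |

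Under the null, unchanged v chemotherapy is 1.04-1.25, while the whole-arm comparison stays at 1.00-1.01.

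**Increases and decreases together.** A separate simulation at trial size used censoring uniform over 6-30 months, 30-50% of subjects as candidates for an increase in months 1-2 or 1-4, and decreases at 3-6% per month. The null hazard ratios against chemotherapy were 0.70-0.80 (increased), 0.60-0.63 (decreased) and 1.22-1.49 (unchanged). The whole arm stayed at 1.00.

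**Does a repair remove the artefact?** Under random change, within the ASP2215 arm, a time-dependent covariate gives 0.995-1.003 and a 2-month landmark 0.992-1.006.

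**Change that is not random.** Null case, 40% responders, only non-responders change dose (60% of those eligible). With a non-responder hazard 1.5, 2 or 2.5 times that of responders, changed v chemotherapy is 0.96, 1.07 or 1.18 for months 1-2 and 0.85, 0.95 or 1.04 for months 1-4.

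**The case against.** - **No decision depends on it.** The split is absent from Table 4 and from the decision rules in Section 7.10. Version 4.0 plans no further efficacy analysis, since results at the 17 SEP 2018 cutoff are already reported. This stands and limits the weight of the point. The item nevertheless remains in the plan as a sensitivity analysis of a co-primary endpoint.
- **The sizes are assumed.** The dose rules are in the protocol, which is not shown. One dated trigger in the SAP, Table 1 footnote s, places a decision at about cycle 1 day 10, "in which the investigator should assess if the ASP2215 dose modification should occur as per the dose interruption or reduction guideline"; that timing fits the mildest scenario. Footnote e allows QTcF-driven changes at any time point, so later windows are possible, but nothing in the SAP supports a particular one. This stands: the error rates are illustrations.
- **The comparator is not stated.** True, and much of the table assumes chemotherapy. The changed v unchanged column shows that the artefact is larger if the dose groups are compared with each other.
- **The repair can look worse.** In the non-responder null, the unrepaired within-arm ratio is 0.94, 1.09 or 1.21 for months 1-2, while a 2-month landmark gives 1.32, 1.62 or 1.89. The arithmetic is right. The unrepaired figure lies nearer 1 only because immortal time and confounding offset each other, and that balance cannot be relied on. The repair removes the structural error and leaves the confounding visible.
- **Other contrasts are weak.** Section 7.4.6 first calls the CR/CRh work descriptive, although it then names a CMH test. The Section 7.1 rule, "For subjects with dose increase/decrease, actual treatment refers to the initial dose received before dose change", concerns as-treated summaries, so it does not contradict an ITT analysis. Both are fair and neither is needed for the conclusion.

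**Conclusion.** The concern holds. Classifying subjects by a later dose change while counting OS from randomization makes survival a condition of group membership, whichever comparator is used. The result cannot speak to the robustness of the OS finding. How large the distortion is, and its net direction, depend on when, how often and why doses change. Under random change it favours the changed-dose groups; if change follows poor response it can cancel or reverse. The defect is confined to this split. The ITT primary test, alpha and decision rules are untouched, so the correction is advisable but does not put the primary conclusion at risk.

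**What to change.** 1. Remove the dose-adjustment split from the OS sensitivity list and label it exploratory.
2. Analyse OS by dose within the ASP2215 arm only. One option is dose status (below, at or above the starting dose) as a time-dependent covariate. The other is a fixed landmark, for example day 56, among subjects alive then, classified by changes up to that day, with survival counted from the landmark.
3. State how subjects with both kinds of change, or with no dose, are classified, and that confounding by response or toxicity remains.
4. Report CR and CR/CRh by dose group descriptively, as already planned for CRc, with no test against chemotherapy.
5. Attach this caveat to any output of the split already reported, or reanalyse it and mark the reanalysis as post hoc.

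The cost is one extra program and a caveat or reanalysis. A day-56 landmark (1.84 months) drops subjects who die earlier: 1 − exp(−ln 2 × 1.84/7.7) = 15% at the planned median, or 23% if the median is 5 months. Neither method removes confounding: in the non-responder null, changed v not changed is 1.30-1.83 with the time-dependent covariate and 1.24-1.88 with a 2-month landmark.
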